### ***Bone Marrow Suppression***

In the randomized trial, 2% of patients on the Radium Ra 223 dichloride arm experienced bone marrow failure or ongoing pancytopenia compared to no patients treated with placebo. There were two deaths due to bone marrow failure and for 7 of 13 patients treated with Radium Ra 223 dichloride, bone marrow failure was ongoing at the time of death. Among the 13 patients who experienced bone marrow failure, 54% required blood transfusions. Four percent (4%) of patients on the Radium Ra 223 dichloride arm and 2% on the placebo arm permanently discontinued therapy due to bone marrow suppression.

In the randomized trial, deaths related to vascular hemorrhage in association with myelosuppression were observed in 1% of Radium Ra 223 dichloride-treated patients compared to 0.3% of patients treated with placebo. The incidence of infection-related deaths (2%), serious infections (10%), and febrile neutropenia (< 1%) were similar for patients treated with Radium Ra 223 dichloride and placebo.

Myelosuppression; notably thrombocytopenia, neutropenia, pancytopenia, and leukopenia; has been reported in patients treated with Radium Ra 223 dichloride. In the randomized trial, complete blood counts (CBCs) were obtained every 4 weeks prior to each dose and the nadir CBCs and times of recovery were not well characterized. In a separate single-dose phase 1 study of Radium Ra 223 dichloride, neutrophil and platelet count nadirs occurred 2 to 3 weeks after Radium Ra 223 dichloride administration at doses that were

up to 1 to 5 times the recommended dose, and most patients recovered approximately 6 to 8 weeks after administration.

In the radium-223 arm of the Phase 3 clinical trial reported in Parker et al. (2013), 12.7% (76 / 600) of subjects had grade 3+ anemia, 6.5% (39 / 600) of subjects had grade 3+ thrombocytopenia, and 2.2% (13 / 600) of subjects had grade 3+ neutropenia.

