#### **9.3.1 Interim Analysis for Safety**

There will be no formal interim analysis of the efficacy data.

An interim analysis of the safety data will be conducted during the study. The interim analysis will be conducted when 10 subjects have completed treatment with 6 injections of radium-223 dichloride or discontinued study treatment early. The purpose of this interim analysis is to formally review safety data and to assess whether it is acceptable to continue enrollment of subjects. The review of the safety data in this interim analysis will be conducted by the HCI Data Safety Review Committee (DSMC). A proportion of subjects with grade 3 or higher hematologic adverse events significantly more than those reported for the radium-223 arm of the Phase 3 trial would be evidence of unacceptable toxicity. In particular, four or more grade 3+ anemias, three or more grade 3+ thrombocytopenias, or three or more grade 3+ neutropenias in ten subjects would be statistically significantly higher than expected (at the one-sided 0.05 significance level). An adjustment may be made to these numbers if the proportion of patients with prior chemotherapy is higher than the 59% reported in Parker et al (2013).

A final safety analysis will be conducted when all 35 evaluable subjects have completed 6 doses of treatment, plus the end of treatment visit (30 days post-last dose), or discontinued treatment early.

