#### **10.1.3 Primary Safety Analyses**

An overall proportion of subjects with grade 3 or higher hematologic adverse events significantly higher than those reported for the radium-223 arm of

Parker et al. (2013) would be evidence of unacceptable toxicity. The sum of the proportion of subjects in Parker et al. (2013) with grade 3+ anemia, thrombocytopenia, or neutropenia is 21%. An exact binomial test will be performed at the one sided 0.05 significance level comparing the proportion of subjects with one or more of grade 3+ anemia, thrombocytopenia, or neutropenia to 21%. With a safety population of 35 evaluable patients, 13 or more patients with one or more of grade 3+ anemia, grade 3+ thrombocytopenia, or grade 3+ neutropenia would indicate an unacceptable hematologic adverse event rate.

Exact 90% confidence intervals will be calculated for adverse events and serious AEs. With 35 evaluable patients an exact 90% confidence interval for an AE will extend no more than 17.5% from the observed proportion, and there is a 90% probability that an adverse event with a probability of 6.4% will be observed at least once.

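### The interim safety look has numeric limits for each cytopenia but none for patients with any cytopenia, so 5 or 6 affected patients of 10 can cross no listed limit although either count would be significant on the final rule's endpoint.

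*Combined protocol and SAP*

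**What the plan says.** Section 9.3.1 schedules one safety review "when 10 subjects have completed treatment with 6 injections of radium-223 dichloride or discontinued study treatment early", to decide whether enrollment may continue. It opens with a general criterion, treated as a sign that toxicity is too high: "A proportion of subjects with grade 3 or higher hematologic adverse events significantly more than those reported for the radium-223 arm of the Phase 3" (the reference study). It then gives its only numbers, "four or more grade 3+ anemias, three or more grade 3+ thrombocytopenias, or three or more grade 3+ neutropenias in ten subjects", and says that these "would be statistically significantly higher than expected (at the one-sided 0.05 significance level"). It allows the numbers to be adjusted if more patients than the reference 59% have had prior chemotherapy.

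The final rule (10.1.3, repeated in the Study Summary) uses a different unit. It is an exact one-sided binomial test at 0.05, "comparing the proportion of subjects with one or more of grade 3+ anemia, thrombocytopenia, or neutropenia to 21" per cent, with 13 or more of 35 patients unacceptable. The 21% is described there as the sum of the three separate proportions in the reference trial.

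The reference rates are in section 3.1.4 under Bone Marrow Suppression. For anemia the text gives "12.7% (76 / 600) of subjects had grade 3+ anemia"; the matching figures are 39/600 (6.5%) for thrombocytopenia and 13/600 (2.2%) for neutropenia.

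**The concern.** The interim and final criteria address the same toxicity but count it differently. The interim numbers count each cytopenia by itself; the final test counts patients with at least one. Affected patients spread over the three types can stay below every interim limit while the number of affected patients is already significantly high on the final endpoint.

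This is the plan's one formal safety look before the end, and its purpose is to decide on further enrollment. If the committee works from the listed counts, the pattern most relevant to the final test has no prespecified signal.

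**Working it through.** **1. The plan's interim limits.** For n = 10, P(X ≥ r) = Σ C(10,k) p^k (1−p)^(10−k), summed over k from r to 10.

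- Anemia, p = 76/600 = 0.1267: P(X ≥ 4) = 0.029; P(X ≥ 3) = 0.123.
- Thrombocytopenia, p = 39/600 = 0.065: P(X ≥ 3) = 0.023; P(X ≥ 2) = 0.134.
- Neutropenia, p = 13/600 = 0.0217: P(X ≥ 3) = 0.001.

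All three counts are below 0.05, as the plan states.

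**2. How many patients can be affected with no limit crossed.** The largest counts below the limits are 3, 2 and 2. In different patients:

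- 5 affected: 3 anemia + 2 thrombocytopenia.
- 6 affected: 3 + 2 + 1.
- 7 affected: 3 + 2 + 2, the maximum.

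**3. The same counts on the final rule's endpoint.** With p = 0.21 and n = 10:

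- P(X ≥ 4) = 0.139.
- P(X ≥ 5) = 0.0317 (exactly 5: 252 × 0.21^5 × 0.79^5) + 0.0082 (6 or more) = 0.040.
- P(X ≥ 6) = 0.008.
- P(X ≥ 7) = 0.001.

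The smallest significant count is therefore 5 of 10. With the unrounded sum, (76 + 39 + 13)/600 = 128/600 = 21.33%, it is still 5 (P = 0.042).

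**4. How soft the 21% is.** A sum of three rates equals the any-cytopenia rate only if no patient has two. With overlap the reference rate is lower, down to 12.67% if every affected patient had anemia. At 12.67%, 5 of 10 gives P = 0.005. Overlap therefore makes 5 of 10 stronger evidence than P = 0.040 suggests.

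**5. What a limit of 5 of 10 would add.** The documents give no joint distribution, so overlap has to be assumed. Each patient is assigned a joint pattern with the three marginal rates above: no overlap, independence, or correlated normal latent variables (ρ) cut at those rates. The distribution over 10 patients is then enumerated exactly. Doubled means all three rates multiplied by 2. Each arrow runs from the listed limits alone to the listed limits plus 5 of 10.

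| Overlap assumed | Alert chance, reference rates (%) | Alert chance, doubled rates (%) | Doubled: ≥5 affected, none crossed (%) | Doubled: ≥6 (%) | Doubled: 7 (%) |
|---|---|---|---|---|---|
| None | 5.29 → 7.10 | 35.6 → 49.4 | 13.8 | 2.8 | 0.25 |
| Independent | 5.24 → 6.42 | 33.8 → 40.5 | 6.7 | 0.84 | 0.04 |
| ρ = 0.3 | 5.14 → 5.75 | 32.3 → 35.5 | 3.1 | 0.24 | 0.01 |
| ρ = 0.5 | 5.01 → 5.30 | 31.1 → 32.5 | 1.4 | 0.06 | <0.01 |
| ρ = 0.7 | 4.79 → 4.88 | 29.6 → 29.9 | 0.4 | 0.01 | <0.01 |

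The practical gap is at 5 affected patients, less often 6. Seven is an extreme.

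**The case against.** The strongest reply is that the listed counts are particular instances of the general criterion in 9.3.1. That criterion already speaks of the proportion of subjects with grade 3 or higher hematologic events, so 5, 6 or 7 of 10 would fall under it. Section 13.3 adds quarterly full-committee review of serious events and related grade 3 or higher toxicities, and provides for stopping the study over unexpected safety concerns. No count by itself passes or stops the trial. All of this stands, and it limits the weight of the point. It does not remove it, because the general criterion has no number for the any-cytopenia proportion and the counts given are the only ones a reviewer can apply directly.

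Separate limits are also a legitimate choice: they can detect an excess of a rarer cytopenia that a composite dilutes. With clustering they do better alone than the composite alone (at ρ = 0.3 and doubled rates, 32.3% against 23.7%). Some clustering is plausible, since section 3.1.4 reports pancytopenia and bone marrow failure with radium-223. This is a reason to keep the listed limits and to expect a modest gain from the addition.

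A reader might infer that the interim look would wave through a cohort with 7 of 10 affected. The documents do not support that. The pattern has a probability of at most about 0.25% at doubled rates, and the general criterion and the committee's powers would still apply to it.

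**Conclusion.** The mismatch is real and follows directly from the text. The interim numbers are per cytopenia, the final rule is per patient with any cytopenia, and 5 or 6 affected patients of 10 can cross no listed limit although each is significant against the plan's own 21%. The gap is in the numeric limits and not in safety oversight as a whole; nor are the listed limits miscalculated.

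Its size depends on overlap, which the documents do not give. At doubled rates, 5 or more affected with nothing crossed occurs in 13.8% of looks with no overlap, 6.7% under independence and 3.1% or less at ρ of 0.3 and above. Doubling is an illustrative assumption. The claim that 5 and 6 of 10 can pass needs no such assumption. The change is worth making because it is cheap, but its priority is modest.

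**What to change.** Keep the three listed limits and add to 9.3.1, as a signal for committee review: 'or five or more of the ten subjects with any grade 3+ anemia, thrombocytopenia or neutropenia (exact one-sided P = 0.040 against 21%)'. Add a note that 21% is a sum of three rates, hence an upper bound on the any-cytopenia reference rate if patients overlap. State that any adjustment for prior chemotherapy applies to this count as well.

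The cost is one or two sentences and slightly more false alerts. At the reference rates the alert chance goes from about 5% to 5.3% (ρ = 0.5), 6.4% (independent) or 7.1% (no overlap). The independence figure should not be read as a ceiling; the largest increase is 7.10 − 5.29 = 1.8 percentage points. Sample size, data collection and the final test are unchanged.

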### **9.4 Efficacy**

#### **9.4.1 Pre-study Documentation of Progressive Disease**

Patients must have documented PD either by radiographic or PSA criteria as defined in Inclusion Criterion # 5.1.6 in Section 5.1.

Both radiographic PD and PSA PD must be assessed to evaluate eligibility; however, only one criterion (radiographic PD or PSA PD) must be met for Inclusion Criterion # 5.

PSA will be assessed at time points shown in the Schedules of Events.

Scans (CT/MRI) of the abdomen and pelvis and radionuclide bone scans will be used to monitor and assess disease response and progression, as described in the Schedule of Events. CT imaging of the chest is only required at baseline if clinically indicated. If disease is found in the chest, lesions should be followed by CT scan. The imaging modality for each patient must remain constant throughout the study. Additional scans should be performed at the

investigator's discretion if progression is suspected or to confirm the existence of bone lesions.

During the protocol specified treatment, disease progression will be defined per PCWG2 progression criteria. After completion of protocol defined therapy, the progression will be defined per clinical discretion of the treating clinician. Patients who complete study treatment without documented disease progression will continue to be followed by scans and PSA per the follow-up outlined in the study calendar until progression is seen or new treatment is started. All patients, regardless of date of progression, will be followed for 2 years post study enrollment for overall survival.

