## STUDY SUMMARY

Title	A Phase 2 Randomized Study comparing Radium Ra 223 dichloride + Enzalutamide with Enzalutamide alone in Men with Metastatic Castration Refractory Prostate Cancer
Short Title	Radium Ra 223 dichloride + Enzalutamide with Enzalutamide alone in mCRPC
Protocol Number	IRB # 68770
IND	IND Exempt (121340)
Phase	Phase 2
Design	Open label, randomized two arm study in men with progressive metastatic CRPC who are candidates for treatment with enzalutamide alone or enzalutamide + Radium Ra 223 dichloride
Study Duration	3.5 years
Study Center(s)	Single-center - Huntsman Cancer Institute
Objectives	
Primary:
 
 
1. To measure the difference between the levels of markers of bone formation (Procollagen Type 1 intact N-terminal Propeptide [NTP] and bone alkaline phosphatase [BAP]) and resorption (N-telopeptide [NT], C-Telopeptide beta-cross linked [CTB], pyridinoline) in serum collected at baseline (C1D1), C3D1, C5D1, EOT and at disease progression (whichever comes earlier) in two arms.
 
2. To establish safety and feasibility of combining enzalutamide and radium-223.
 
 
Secondary:
 
The secondary objectives will compare the two arms for the following:
 
 
1. Time to progression in serum PSA, total ALP concentrations, and radiological progression.
 
2. Response rates by serum PSA, total ALP concentrations.
 
3. Time to first skeletal related event.
 
4. Percent change in opioid use (morphine equivalent) during protocol treatment.
 
5. Overall Survival at 2 years post enrollment.
 

Number of Subjects	47 patients (50 total to account for any inevaluable patients). Combination Arm – 35 evaluable patients (27 randomized patients + 8 patients enrolled prior to randomization who will be used for secondary and exploratory analyses only). Control Arm (enzalutamide alone) – 12 evaluable patients.

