#### 4.4 Duration

It is expected that all patients will be accrued within 18 months. Subjects will remain on study treatment for up to 6 months. Patients will be followed for a total of two years from the first day of protocol treatment or until death, whichever occurs earlier. The total study duration for a patient is expected to be 2 years from the time of enrollment.

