## 6.6 Protocol specified Duration of Therapy

Patients will receive up to 6 cycles of single agent enzalutamide or Radium Ra 223 dichloride and enzalutamide. If patients have a radium cycle delayed, the study visits will continue per the calendar and the dose will be missed. Treatment may be discontinued earlier if one of the following below criteria is met.

Subjects **must be withdrawn from the trial** (during protocol treatment and follow-up) for the following reasons:

- Subject withdraws consent from study treatment and study procedures. A subject must be removed from the trial at his / her own request or at the request of his / her legally acceptable representative. At any time during the trial and without giving reasons, a subject may decline to participate further. The subject will not suffer any disadvantage as a result.
- Subject is lost to follow-up.
- Anti-cancer therapy not prescribed by the study protocol is required.
- A treatment delay of more than 9 weeks between 2 injections of Radium Ra 223 dichloride.
- Disease Progression. During the protocol specified treatment, disease progression will be defined per PCWG2 progression criteria. After protocol defined therapy, the progression will be defined per clinical discretion of the treating clinician.
- Death.

Subjects **may be withdrawn from the study** for the following reasons:

- The subject is non-compliant with study drug, trial procedures, or both.

- If, in the investigator's opinion, continuation of the trial would be harmful to the subject's well-being.
- Development of a second cancer (other than superficial skin cancers, such as squamous cell carcinoma or basal cell carcinoma).
- Development of an intercurrent illness or situation which would, in the judgment of the investigator, significantly affect assessments of clinical status and trial endpoints.
- Deterioration of ECOG performance status to 4.
- Use of illicit drugs or other substances that may, in the opinion of the investigator, have a reasonable chance of contributing to toxicity or otherwise skewing trial result.

In all cases, the reason for withdrawal must be recorded in the CRF and in the subject's medical records.

A subject who discontinues study participation prematurely for any reason is defined as a "dropout" if the subject has already been enrolled / registered.

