## 8 STUDY CALENDAR

1 cycle = 28 days

- 1 ALL Pre-study / Screening procedures should be completed within 4 weeks of study enrollment - with the exception of laboratory tests which need to be completed within 2 weeks prior to study enrollment.
- 2 Hematology includes CBC with differential and platelets. CBC must be completed within 2 weeks of study enrollment and prior to treatment ( $\pm$  7 days) on day 1 of each cycle.
- 3 Chemistry includes Albumin, Alkaline Phosphatase, Aspartate Aminotransferase, Alanine Aminotransferase, Total Bilirubin, Calcium, Carbon Dioxide, Creatinine, Chloride, Glucose, Potassium, Protein, Sodium, and Urea Nitrogen.
- 4 Bone alkaline phosphatase (BAP) should be done every four weeks until the end of treatment visit or disease progression (whichever comes earlier).
- 5 PSA is required within 28 days at screening, on day 1 of each cycle and at the end of treatment visit. PSA laboratory assessments should be performed every 4 – 6 weeks after the end of treatment visit until disease progression, or the start of another treatment.
- 6 CT and bone scans should be conducted at screening, end of cycle 3 (prior to C4D1 treatment), and at the end of treatment visit (4 weeks post last treatment). Follow-up scans will be performed as clinically indicated until documented PD per treating clinician or until the start of another treatment. Scans should include CT scan of abdomen and pelvis. Imaging of the chest is only required if clinically indicated.
- 7 Bone markers collected at baseline (C1D1), C3D1, C5D1, EOT and at disease progression (whichever comes earlier); to include procollagen Type 1 intact N-terminal Propeptide (NTP) and resorption (N-telopeptide [NT], C-Telopeptide beta-cross linked [CTB] and pyridinoline).
- 8 Radium Ra 223 dichloride 55 kBq/kg\*\* on day 1 of every cycle for up to 6 cycles (\*\* 50 kBq/kg prior to implementation of the NIST update).
- 9 Enzalutamide 160 mg daily.
- 10 End of Treatment visit should be conducted 4 weeks post C6D1.
- 11 For all patients who receive study treatment, follow-up for survival will occur approximately every 8 weeks following end of treatment or as clinically indicated for up to 2 years post enrollment or death.
- 12 All procedures for day 1 of each treatment cycle have a  $\pm$  7 day window.
- 13 Subjects receiving concomitant medication with warfarin should have INR monitored more frequently as clinically indicated.

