### 9.4.6.2 Post baseline Assessments and Definition of Progression of Bone Metastatic Disease Based on Radionuclide Bone Scan

Bone scan lesions should be assessed and enumerated at each follow-up assessment.

Progression on bone scan is defined as 2 or more new lesions on radionuclide bone scans. Should 2 or more new bone lesions be evident at the first assessment on treatment (end of cycle 3), 2 or more additional new lesions must be evident on a confirmatory assessment at least 6 weeks later (and no sooner than end of cycle 6). This confirmation is not required when 2 or more new lesions (compared to baseline or to the end of cycle 3 assessment) first appear after the first follow-up assessment, ie, at end of cycle 6 or thereafter.

Should new bone lesions be documented at end of cycle 3 but not confirmed at end of cycle 6, then end of cycle 3 scan becomes the new baseline and 2 or more new lesions at subsequent assessments relative to end of cycle 3 defines bone scan progression.

Stable disease (SD) on bone scan stable disease is defined as the absence of progression. Bone scan lesions are considered non-evaluable under RECIST, and thus there can be no partial response. Complete response is very rare. Thus, almost all bone scans will be rated as NE (no lesions present), SD, or PD.

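### After protocol therapy the plan gives two conflicting rules for progression, so time to radiological progression and rPFS could mix two event definitions in an open-label trial

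*Combined protocol and SAP*

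**What the plan says.** The Study Summary describes an "Open label, randomized two arm study in men with progressive metastatic CRPC". Section 4.4 adds: "Subjects will remain on study treatment for up to 6 months", with two years of follow-up in all.

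Three places change the progression rule when treatment ends:

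- Section 9.4.1: "During the protocol specified treatment, disease progression will be defined per PCWG2 progression criteria". Then: "After completion of protocol defined therapy, the progression will be defined per clinical discretion of the treating clinician".
- Section 6.6, among the withdrawal criteria: "After protocol defined therapy, the progression will be defined per clinical discretion of the treating clinician".
- Section 8, note 6, sets the scheduled scans: "CT and bone scans should be conducted at screening, end of cycle 3 (prior to C4D1 treatment), and at the end of treatment visit". Later scans have no interval: "Follow-up scans will be performed as clinically indicated until documented PD per treating clinician or until the start of another treatment".

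Three places give radiographic criteria without a time limit:

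- Section 9.4.2 applies PCWG2 to radiographic assessment, with RECIST 1.1 for soft tissue.
- Section 9.4.3 requires disease status at every evaluation to follow that section's own categories.
- Section 9.4.6.2: "Progression on bone scan is defined as 2 or more new lesions on radionuclide bone scans". It covers new lesions first seen at the end of cycle 6 and later.

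Time to radiological progression is a secondary objective compared between arms (Section 1.2.1). Sections 10.2 and 10.3 list rPFS and time to radiological bone progression as exploratory variables summarised by Kaplan-Meier.

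**The concern.** A Kaplan-Meier curve assumes that the event means the same thing at every time point. Here a patient on treatment progresses in bone by a lesion count with a confirmation rule, and in soft tissue by a measured increase. If Section 9.4.1 governs, the same patient after treatment progresses when the treating clinician says so. That clinician knows the arm, and no section provides central or blinded reading.

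With only 12 randomised controls against 27 combination patients, a few events called to a different standard could move a median. The clinician's call also ends scan follow-up under note 6, so progression by the criteria may never be observed in that patient. If the choice of rule is left until the open-label data are in hand, the choice itself becomes a source of bias.

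**Working it through.** The plan states no event count, power or median for the radiological endpoints, so there is no figure to reproduce. The check is textual, with arithmetic only for scale.

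**Do the passages conflict?** Section 9.4.6.2 gives the clearest test.

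1. If new bone lesions at the end of cycle 3 are not confirmed at the end of cycle 6, the cycle 3 scan becomes the new baseline. Two or more further lesions at later assessments then define progression.
2. The last scheduled scan is at the end-of-treatment visit, four weeks after day 1 of cycle 6 (Section 8, notes 6 and 10).
3. For a patient who completes treatment, those later assessments are therefore post-treatment scans.
4. If clinician discretion governs post-treatment scans, this rule has nothing to act on. If the rule does act, discretion does not govern. Both cannot date the same event.

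**Does another section settle it?** Section 9.4.8 is headed Progression Free Survival but defines PSA and total ALP events only. No section defines the rPFS event or censors radiological endpoints at end of treatment. Section 9.4.1 continues scans after treatment until progression or new therapy. Section 10.3 defers further censoring details to an SAP, and the document reviewed contains no such text.

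**How much follow-up is involved?** Treatment is 6 × 28 = 168 days = 24 weeks. Two years is 2 × 365.25 / 7 = 104.36 weeks. PCWG2 is unambiguously in force for 24 / 104.36 = 23% of that window, with scheduled post-baseline scans at about weeks 12 and 24.

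**What share of events could be affected?** Assume an exponential time to progression with median m months, everyone completing 24 weeks (168 / 30.4375 = 5.52 months), and no other censoring. Then S(t) = 0.5^(t/m), and the share of 24-month events falling after week 24 is [S(5.52) − S(24)] / [1 − S(24)].

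| Assumed median (months) | S(5.52) | S(24) | Share after week 24 | Late events among 12 controls |
|---|---|---|---|---|
| 6 | 0.529 | 0.063 | 0.466 / 0.938 = 50% | 12 × 0.466 = 5.6 |
| 9 | 0.654 | 0.157 | 0.496 / 0.843 = 59% | 12 × 0.496 = 6.0 |
| 12 | 0.727 | 0.250 | 0.477 / 0.750 = 64% | 12 × 0.477 = 5.7 |
| 18 | 0.809 | 0.397 | 0.412 / 0.603 = 68% | 12 × 0.412 = 4.9 |

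The medians are assumptions. Scan follow-up stops at the start of another treatment, which would lower these shares. Patients who stop treatment early would meet the switch before week 24.

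**The case against.** The best defence is that the discretion sentences and the radiographic sections do different jobs. In Section 6.6 the sentence sits among withdrawal reasons, and in note 6 it says when follow-up scans stop. On that reading clinician judgement ends follow-up, while Sections 9.4.2 to 9.4.7 classify every scan. This is tenable, and it rules out a stronger inference that a reader might draw: that late radiological events have no common definition at all. Criteria exist and carry no end date. But Section 9.4.1, within the efficacy criteria, says that discretion defines progression, so the documents do not establish the benign reading either.

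Two further limits stand. Section 10.2 makes all non-primary analyses descriptive, and only time to radiological progression is a named secondary objective. The deferred SAP might also censor at the end-of-treatment scan. That would limit the problem, but it cannot be confirmed from the text available.

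A reader might also compute the share still progression-free at month 6, for example 0.5^(6/9) = 63% or 0.5^(6/12) = 71%, and read it as the share of events under the discretionary rule. It is a share of patients, some of whom will not progress within 24 months. The table gives the share of events.

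**Conclusion.** The conflict is real and should be resolved before event dates are analysed. Sections 6.6, 8 (note 6) and 9.4.1 point to clinician discretion after therapy; Sections 9.4.2, 9.4.3 and 9.4.6.2 point to PCWG2 and RECIST 1.1. Following Section 9.4.1 as written would mix two definitions in one between-arm summary. Roughly half to two thirds of 24-month events could be involved, on assumed exponential medians of 6 to 18 months with no censoring at new treatment.

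The consequence is Kaplan-Meier summaries that are hard to interpret and open to bias. The documents do not support calling them uninterpretable. Nor do they support extending the point to the primary result: N-telopeptide change is taken at end of treatment or earlier progression, so planned assessment falls within the PCWG2 period. PSA progression keeps the numeric rule in Section 9.4.8. No error rate or sample size changes.

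**What to change.** Reconcile Sections 6.6, 8 (note 6) and 9.4.1 with Sections 9.4.2, 9.4.3 and 9.4.6.2 by adding an analysis rule:

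- Radiological progression, radiological bone progression and the radiographic component of rPFS use the criteria in Sections 9.4.5 to 9.4.7 throughout follow-up, applied to whatever scans are obtained. State also how deaths enter rPFS, since no section defines that event.
- Progression declared by the clinician without qualifying scans is reported separately by arm. For the radiological endpoints such patients are censored at the last evaluable scan.
- Because that censoring may be informative, add a sensitivity analysis that either counts clinician-declared progression as an event or censors everyone at the last protocol-scheduled (end-of-treatment) scan.

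The cost is wording, plus applying existing criteria to scans already done. No new scans or patients are needed, and treatment decisions do not change. The fix leaves two weaknesses: post-treatment scan timing remains irregular and at the clinician's choice, and all reads remain unblinded. Both should be stated when the results are reported.
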